2.3 Endpoints

Primary endpoints are ARFI PD and TD, VisR τ , RE, RV and RM, and DDAI degree of anisotropy measured as the ratio of PD and as the ratio of RE values. The secondary endpoints are changes in these eight ultrasound-derived metrics over time. These primary and secondary endpoints will be used for Aims #1 and #2 objectives listed above.

3.0 PATIENT ELIGIBILITY

In Aim #1, patients will be recruited from those who have undergone breast imaging and are indicated for biopsy according to the routine standard of care at UNC Hospitals. Both diagnostic imaging and biopsy will be performed according to institutional standards and will not be altered for research purposes. In addition to standard radiologic examinations, the patients will undergo ARFI, VisR, and DDAI ultrasound imaging prior to standard of care biopsy..

In Aim #2, patients will be recruited from those already undergoing NAC for treatment of breast cancer according to the standard of care at UNC Hospitals. NAC will be performed based on institutional standards and will not be altered for research purposes, except that we will perform serial ultrasound imaging over the course of treatment. The standard for clinical management during and after NAC will not be altered.

Potential study participants will be patients 30-90 years of age who have been diagnosed by their treating physician to have a BIRADS breast assessment categories of -4a, 4b, 4c, or -5 breast lesion (Aim #1) or to be in need of NAC for the treatment of breast cancer (Aim #2). All patients will be recruited from and imaged at the University of North Carolina Hospitals. Based on local demographics, we estimate that roughly 20% will be racial and ethnic minorities. Children are not likely to have breast cancer and will not be included in this study.

We will enroll participants in two groups, as patients with suspicious (Aim #1) breast lesions, or as patients with confirmed breast cancer undergoing clinically indicated NAC (Aim #2). There will be no randomization to study arms and no intervention beyond ARFI, VisR, and DDAI ultrasound imaging.

3.1 Inclusion Criteria

Subjects must meet all of the inclusion criteria for either Aim 1 or Aim 2 in order to participate in this study.

3.1.1 Aim 1

3.1.1.1 Patients are aged 30-90 years

3.1.1.2 Patients with BIRADS 4a, 4b, 4c, or 5 rating

3.1.1.3 Lesion is sonographically visible with B-Mode ultrasound on diagnostic workup

3.1.1.4 Informed consent obtained and signed

3.1.2 Aim 2

3.1.2.1 Patients are aged 30-90 years

3.1.2.2 Patients who are or will be undergoing neoadjuvant chemotherapy (NAC) for TNM staging of T1-T4, N0-N3 and M0-M1

3.1.2.3 Lesion is sonographically visible with B-Mode ultrasound on diagnostic workup

3.1.2.4 Informed consent obtained and signed

3.2 Exclusion Criteria

Subjects who meet any of the exclusion criteria will be excluded from study participation for both Aim 1 and Aim 2. (With the exception for Aim 2 – 3.2.5, since those subjects would have had a biopsy-proven malignant lesion).

3.2.1 Inability to provide informed consent

3.2.2 Inability to communicate in English

3.2.3 Inability to remain motionless for 15 minutes

3.2.4 Suspicious or malignant breast mass deeper than 3 cm from skin surface

3.2.5 Aim 1 - Previous biopsy or surgery to the site of the suspicious or malignant mass. Aim 2 – Surgical excision of biopsy-proven lesion of interest.

3.2.6 Patients who are pregnant

[figure not shown]
3.2.7 Patients who are lactating

3.2.8 Patients with a history of mastectomy

3.2.9 Patients with breast implants

4.0 STUDY PLAN

4.1 Schema

4.2 Imaging Schedule

Study enrollment will occur for approximately 18 months, with anticipated recruitment of 4-5 patients per month. Total ultrasonic imaging time for all imaging conditions (ARFI, VisR, DDAI) is approximately 15 minutes. Therefore, Subjects participating in Aim 1 of the study will participate for an expected duration of 15 minutes. Subjects participating in Aim 2 will be participating for an expected duration of approximately 15 minutes per imaging session during the duration of their NAC treatment as outlined in Section 4.2.2.

4.2.1 Arm 1

In addition to standard radiologic examinations, the patients will undergo ARFI, VisR, and DDAI ultrasound imaging after BIRADS diagnosis but prior to biopsy.

4.2.2 Arm 2

Patients in Arm 2 will be imaged to align with their clinical treatment schedule. Imaging will occur at baseline, at 2 – 3 weeks (+/- 7 days) into therapy (driven by treatment plan), and at completion of each chemotherapy type. In some cases, the final US of one chemotherapy type will also serve as the baseline for the next regimen. The below schedule has been included for clarity and as an example. Patients undergoing any NAC regimen will be included and their imaging will align with their treatment at baseline, early treatment by chemotherapy type, and the end of each chemotherapy type. In the event that subjects undergo more than 3 rounds of chemotherapy, an additional scan will be completed at the end of all chemotherapy. At minimum, patients would undergo 3 US scans, and at maximum of 8 US scans.

	Baseline Chemotherapy Type 1	Early Chemotherapy Type 1	Completion of Chemotherapy Type 1/ Baseline Chemotherapy Type 2	Early Chemotherapy Type 2	Completion of Chemotherapy Type 2/ Baseline Chemotherapy Type 3	Early Chemotherapy Type 3	Completion of Chemotherapy Type 3
ER+/HER2-	day 0	day 14 (+/- 7 days)	end of chemotherapy type (+/- 7 days)	day 14 (+/- 7 days)	end of chemotherapy type (+/- 7 days)	day 14 (+/- 7 days)	end of chemotherapy type (+/- 7 days)
TNBC	day 0	day 14 (+/- 7 days)	end of chemotherapy type (+/- 7 days)	day 21 (+/- 7 days)	end of chemotherapy type (+/- 7 days)	day 14 (+/- 7 days)	end of chemotherapy type (+/- 7 days)
HER2+	day 0	day 14 or 21 (+/- 7 days) depending on treatment schedule	end of chemotherapy type (+/- 7 days)	day 21 (+/- 7 days)	end of chemotherapy type (+/- 7 days)	N/A	N/A

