6.0 STATISTICAL CONSIDERATIONS

6.1 Study Design/Study Endpoints

For Aims #1 and #2, the ability of ultrasound biomarkers to discriminate binary outcomes (malignant/benign and responsive/unresponsive to treatment) will be analyzed using logistic regression. The area under the receiver operating characteristic curve (AUC) will be quantified, with separate models fit for each of the eight ultrasound biomarkers. Because most ultrasound biomarkers are continuous measures, the best-balanced cutpoints optimizing sensitivity and specificity will be calculated, using Youden's Index. Outcome discrimination by dual biomarkers will be analyzed in 28 separate models with combinations of any two ultrasound biomarkers. The combined benefit of ultrasound and mammography will be analyzed in 32 models, by adding a single mammography metric (lesion size, density, shape, or margins) to each of the eight ultrasound biomarker models. In Aim #2, the relationship between biomarker values and tumor size, biomarker values and change in tumor size, and change in biomarker values and change in tumor size will be analyzed by linear regression. These correlations will be analyzed in separate models for each of the eight ultrasound biomarkers, in models of dual ultrasound biomarkers, and in models combining mammography metrics with ultrasound biomarkers.

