6.3.2.1 Which baseline ultrasound metric best predicts positive response to NAC?

Response to NAC will be dichotomized into a yes/no response according to the RECIST guidelines, and the predictive ability of each baseline ultrasound metric will be analyzed by constructing separate ROC curves.

6.3.2.2 Which baseline ultrasound metric correlates most strongly with absolute reduction in tumor size (diameter, area, volume)?

The relationship between ultrasound metric values at baseline and absolute change in tumor size from baseline to end of chemotherapy type will be visualized by scatterplots. If the relationship appears linear and monotonic, the correlation will be assessed by Pearson regression.

6.3.2.3 What is the combined ability of any 2 baseline ultrasound metrics for prediction of positive response to NAC?

With response to NAC dichotomized into a yes/no response, the combined predictive ability will be analyzed by constructing separate ROC curves for combinations of any 2 ultrasound metrics.

6.3.2.4 Do serial changes in ultrasound metrics correlate with reduction in tumor size following NAC?

The relationships between serial changes in ultrasound metrics and tumor size will be visualized by scatterplots. If monotonic and linear, the correlation between serial change in ultrasound metrics and change in tumor size (area) will be analyzed by Pearson regression. Assessments of serial change will be made at 3 intervals per chemotherapy type: baseline, early chemotherapy type treatment, and end of chemotherapy type treatment.

6.3.2.5 Serial change in which of the 8 ultrasound metrics best predicts positive response to NAC?

Response to NAC will be dichotomized into a yes/no response, and the predictive ability of serial change in each ultrasound metric from 0-6 weeks will be analyzed by constructing separate ROC curves.

6.3.2.6 Do combinations of changes over time in any ultrasound outcome metrics correlate with reduction in tumor size following NAC?

Assuming linear relationships exists between serial change in ultrasound metrics and serial change in tumor size following NAC, multiple linear regression models will be constructed for each of the 8 ultrasound metrics. The model outcome will be change in tumor size, and model predictors will be serial change in any 2 ultrasound metrics.

6.3.2.7 Which combinations of serial change for any 2 ultrasound metrics best predicts positive response to NAC?

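### Aim 2's pooled AUCs cannot show whether an ultrasound metric predicts response beyond receptor subtype, because no planned model contains subtype or regimen

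*Combined protocol and SAP*

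**What the plan says.** **Who enters.** Section 3.1.2.2 admits "Patients who are or will be undergoing neoadjuvant chemotherapy (NAC) for TNM staging of T1-T4, N0-N3 and M0-M1", with no restriction by receptor subtype. Section 4.2.2 adds "Patients undergoing any NAC regimen will be included and their imaging will align with their treatment at baseline". The example schedule there has one row each for ER+/HER2-, TNBC and HER2+ disease. The first two run to three chemotherapy types; the HER2+ row shows N/A for the third. The early scan is at day 14 or day 21 according to row and type, and the first early scan for HER2+ is "day 14 or 21 (+/- 7 days) depending on treatment schedule".

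**What is modelled.** Section 6.1 describes logistic models "with separate models fit for each of the eight ultrasound biomarkers". It continues: "Outcome discrimination by dual biomarkers will be analyzed in 28 separate models with combinations of any two ultrasound biomarkers". The 32 remaining models are formed "by adding a single mammography metric (lesion size, density, shape, or margins) to each of the eight ultrasound biomarker models". Those four mammographic features are the only covariates that are not ultrasound metrics. For response, 6.3.2.1 says that "the predictive ability of each baseline ultrasound metric will be analyzed by constructing separate ROC curves"; 6.3.2.5 does the same for serial change. Nothing in 6.3.2.1 to 6.3.2.9 stratifies by, adjusts for or tabulates subtype or regimen.

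**What follows from a high AUC.** Under 6.3.2.8, metrics with an AUC above 0.75 go on to be combined with mammography. There is no formal success rule, and 1.4 calls the study exploratory.

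**What is collected.** Section 4.4 has the biopsy pathology report and treatment information abstracted for each patient.

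**The concern.** The plan's own schedule links subtype to treatment and to scan timing. If response rates also differ by subtype, and if a metric's average differs by subtype, the metric will separate responders from non-responders in the pooled sample even when it carries no information among women of the same subtype. None of the planned outputs could reveal this.

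The two kinds of predictor are exposed differently:

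- **Baseline metrics** precede treatment. They are exposed only through subtype or other pre-treatment factors.
- **Serial-change metrics** are also exposed directly to regimen and scan timing, because the change is recorded under different drugs and at different times.

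At stake is how a good AUC is interpreted. The hypothesis is that mechanical properties predict response. A metric that only re-identifies subtype gives a clinician nothing that the pathology report has not already given, and the plan as written could rank it best or carry it forward.

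**Working it through.** **1. The plan's own figure.** Section 6.2 projects 12 non-responders among 40, hence 28 responders (70%), and gives AUC 0.70 with a 95% CI of 0.51 to 0.89. The Hanley-McNeil formula uses Q1 = A/(2−A) = 0.7/1.3 = 0.5385 and Q2 = 2A²/(1+A) = 0.98/1.7 = 0.5765.

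Variance = [0.21 + 11(0.5385−0.49) + 27(0.5765−0.49)]/(12×28) = 3.078/336, so SE = 0.0957 and the CI is 0.512 to 0.888.

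The interval reproduces. The stated 80% power does not at a two-sided 0.05 level (51 to 56%). That is a separate matter, and nothing below depends on it.

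**2. Assumptions.** The documents give neither response rates nor metric values by subtype. I assume three equal subtypes, 70% response overall, within-subtype SD of 1, and a metric unrelated to response within every subtype (true within-subtype AUC 0.50). Subtype means are 0.5 or 1.0 SD apart per step.

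**3. Formula.** Pooled AUC = Σ P(i | responder) × P(j | non-responder) × Φ((μi − μj)/√2), summed over subtypes i and j.

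**4. One case in full: response 40/80/90%, 1.0 SD per step, means rising with response.** Responder shares are 4/21, 8/21 and 9/21. Non-responder shares are 6/9, 2/9 and 1/9.

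| Responder's subtype relative to non-responder's | Share of pairs | Φ | Product |
|---|---|---|---|
| Same | 0.259 | 0.500 | 0.130 |
| One step higher | 0.349 | 0.760 | 0.265 |
| Two steps higher | 0.286 | 0.921 | 0.263 |
| One step lower | 0.085 | 0.240 | 0.020 |
| Two steps lower | 0.021 | 0.079 | 0.002 |

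The sum is 0.680. Subtype alone, with ties counted as half, gives 0.130 + 0.349 + 0.286 = 0.765 in this case.

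**5. All cases.** The last two columns come from 20,000 simulated trials of 40 women per setting. Other orderings are taken in whichever direction exceeds 0.50.

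| Response by subtype | Pooled AUC, aligned (0.5 to 1.0 SD) | Pooled AUC, other orderings (0.5 SD; 1.0 SD) | Pairs within a subtype | AUC > 0.75, aligned | Some subtype has no non-responder |
|---|---|---|---|---|---|
| 60/70/80% | 0.54 to 0.57 | 0.52; 0.54 | 32% | 2 to 4% | 8% |
| 50/75/85% | 0.57 to 0.63 | 0.52 to 0.55; 0.54 to 0.59 | 30% | 4 to 10% | 16% |
| 40/80/90% | 0.61 to 0.68 | 0.52 to 0.58; 0.54 to 0.64 | 26% | 7 to 24% | 30% |

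With 70% response in every subtype, the screen is passed in the same direction in under 1% of trials. These rates are per metric, and the plan screens eight metrics and 28 pairs.

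**6. What stratifying does.** In the same simulations, an AUC counting only within-subtype pairs stays centred on 0.50. Its SD is 0.11 to 0.13, against 0.09 to 0.10 for the pooled AUC. A second set of assumptions (shares 40/30/30%, the first subtype shifted by up to 1.5 SD) agrees. There a pooled rank test rejects in up to 54% of trials and a subtype-stratified rank test in about 5%.

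**7. Power cost.** For a true within-subtype AUC of 0.70, with 16/12/12 women and 4 non-responders in each subtype, power is about 51% stratified and 53% pooled (two-sided 0.05). This even split flatters stratification. The settings with large response differences leave fewer usable pairs.

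**The case against.** The strongest reply is that the plan asks which metric best predicts response, not which adds to subtype. A metric that tracks subtype, when subtype predicts response, really does predict response. A reader might infer that the pooled AUC is biased or invalid; it is not, for the marginal question. That part of the reply stands.

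A reader might also infer that the trial will declare a spurious predictor. The documents do not support this: Aim 2 has no test, alpha or success rule, and the 0.75 threshold only sends a metric on to the mammography models.

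The larger magnitudes are fragile. An AUC near 0.68 needs a 50-point response spread, 2 SD between the extreme subtypes, and subtype means in the same order as response. Other orderings of the 1.0 SD cases give 0.54 to 0.64.

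Nor does the schedule prove a difference in the amount of treatment. It is offered as an example, it counts chemotherapy types rather than duration or dose, and the day 14 and day 21 windows overlap once the 7-day tolerance is applied. Scan timing cannot affect a baseline metric at all.

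Finally, a metric plus two subtype terms leaves 12/3 = 4 non-responders per parameter, too few to carry the conclusion.

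What the reply does not remove is that prediction and subtype marking cannot be told apart from the planned outputs, although the data to separate them are already collected.

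**Conclusion.** The omission is a matter of record: Aim 2 pools every subtype and regimen, and none of its models contains either. The planned AUCs therefore support statements about marginal prediction only. How much this matters cannot be settled from the documents. Under the assumed range, a metric with no within-subtype information shows a pooled AUC of about 0.52 to 0.68. With mild or misaligned subtype differences the inflation is small. With extreme, aligned differences the metric passes 0.75 often enough to mislead. Baseline metrics carry the risk through subtype and other pre-treatment factors; serial-change metrics carry the further risk from regimen and timing. For an exploratory study this is a change that should be made for interpretation, not a flaw that invalidates the analysis.

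**What to change.** In 6.3.2.1 and 6.3.2.5, keep the pooled AUC. For each single metric, or at least for those ranked best or exceeding 0.75, also report:

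- a subtype-only AUC (ER+/HER2-, TNBC, HER2+) as reference;
- a subtype-stratified AUC with its confidence interval, comparing responders with non-responders of the same subtype only;
- as supportive only, a model with the metric and subtype, preferably penalised.

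State in advance that a metric will be said to predict response beyond subtype only if the stratified AUC supports it, and will otherwise be described as a marginal predictor. Do not substitute separate curves per subtype. With 4 or 5 non-responders each, the interval around an AUC of 0.70 would run from about 0.36 to 0.40 up to 1.0.

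**Cost.** Analysis wording and a few extra estimates. Subtype already lays out the example scan schedule, and the pathology report is abstracted under 4.4. Intervals will be wider, since only about 26 to 32% of responder/non-responder pairs fall within a subtype in the settings above. A subtype with no non-responders contributes nothing. Regimen and timing differences within a subtype stay unadjusted and should be stated as a limitation, above all for serial change.

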4.3 Patient Identification and Consent

Informed consent will occur prior to participants receiving any sedation for biopsy or NAC, should it be needed. The informed consent will be a written document explaining procedures and risks of the study. The Investigator will review the consent form with the subject and will answer any questions potential participants might have. Once all questions have been answered, the subject will be asked if they still want to participate, and if so, to sign the consent and HIPAA documents.

4.4 Abstraction of Medical Records (if applicable)

Patient's medical record will be reviewed to assess response to neoadjuvant chemotherapy. We will review each patient's clinical records, including their pathology report from biopsy and information about treatment. Malignancy will be determined as indicated by the pathology report.

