1.0 BACKGROUND AND RATIONALE

1.1 Study Synopsis

The primary objective of the proposed research is to evaluate *in vivo* the diagnostic relevance of ultrasound-derived metrics for stiffness, elasticity, viscosity, and anisotropy. These biomarkers will be measured using novel, noninvasive ultrasound technologies under development in [name] laboratory: 1) Acoustic Radiation Force Impulse (ARFI) ultrasound for interrogating tissue stiffness, 2) Viscoelastic Response (VisR) ultrasound for assessing tissue elasticity and viscosity, and 3) Dynamic Displacement Anisotropy Imaging (DDAI) for measuring tissue anisotropy.

We hypothesize that ultrasound-derived stiffness, elasticity, viscosity, and anisotropy will detect lesion malignancy and predict response to treatment. To test this hypothesis, we will pursue the following specific aims:

Aim #1: Quantify the ability of ultrasound-derived stiffness, elasticity, viscosity, and anisotropy to detect malignancy. ARFI, VisR, and DDAI imaging will be performed on suspicious breast lesions in 40 women with BIRADS-4a, 4b, 4c, or -5 ratings. The diagnostic accuracy of imaging metrics will be analyzed, with malignancy confirmed by histology as the outcome.

Aim #2: Quantify the ability of ultrasound-derived stiffness, elasticity, viscosity, and anisotropy to predict a positive response to treatment. ARFI, VisR, and DDAI imaging will be performed serially over the course of neoadjuvant chemotherapy (NAC) - on malignant breast lesions in 40 women. Changes in outcome metrics over time will be correlated to overall reduction in tumor size (diameter and area). The ability of ultrasound metrics to predict a positive response to treatment will be examined. A positive response to treatment will be determined according to the Response Evaluation Criteria in Solid Tumors (RECIST) guidelines.^{1,2}

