2.0 STUDY OBJECTIVES

The purpose of this study is to evaluate *in vivo* the diagnostic relevance of ultrasound-derived stiffness, elasticity, viscosity, and anisotropy metrics for breast lesion malignancy and response to treatment.

2.1 Aim #1: Quantify the ability of ultrasound-derived stiffness, elasticity, viscosity, and anisotropy to detect malignancy.

In vivo ARFI, VisR, and DDAI imaging will be performed in 40 women with a breast mass with a BIRADS breast assessment categories of -4a, 4b, 4c, or -5 rating after diagnostic workup. First, the transducer will be placed lightly above the suspicious mass, just to the point of skin contact, to avoid pre-compression during imaging.¹⁵ The suspicious mass will be positioned at 10 to 40 mm in axial depth, with standoff used if needed to achieve the desired axial position. Second, the position of the transducer will be rotated through 90° in steps of 30° to identify the transducer position yielding maximum ARFI peak displacement in the mass. The transducer will be stabilized in this position, with light skin contact, by the sonographer or by using a stereotactic clamp. Third, ARFI and VisR data will be acquired in immediate succession. Fourth, the transducer will be rotated 90°, re-stabilized by the sonographer or by using the stereotactic clamp, and ARFI and VisR data will be acquired in the new transducer position to enable DDAI analysis. Finally, the evaluated mass will undergo clinically indicated biopsy with histological evaluation to determine if it is benign or malignant.

The ultrasound data will be processed to calculate the following outcome metrics: peak displacement (PD), displacement at a given time (TD) for ARFI; τ , relative elasticity (RE), relative viscosity (RV), and tissue mass (TM) for VisR; ratio of ARFI PD and ratio of VisR RE values at 90° versus 0° transducer orientations for DDAI. These eight outcome metrics, alone and in combinations, will be statistically correlated with biopsy finding of malignant or benign.

2.1.1 Determine which of the 8 ultrasound metrics best detects malignancy.

We will statistically evaluate all eight ultrasound outcome metrics independently to determine which metric best detects malignant finding.

2.1.2 Determine the combined diagnostic accuracy of any 2 ultrasound metrics.

We will systematically combine all possible groupings of two ultrasound outcome metrics. We will then determine which grouping of metrics best detects malignant finding.

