6.3 Data Analysis Plans

6.3.1 Aim #1: Correlate ultrasound-derived stiffness, elasticity, viscosity, and anisotropy to malignancy.

In vivo ARFI, VisR, and DDAI imaging will be performed in 40 women with a breast mass with a BIRADS breast assessment categories of -4a, 4b, 4c, or -5 rating after diagnostic workup. First, the transducer will be placed lightly above the suspicious mass, just to the point of skin contact, to avoid pre-compression during imaging.¹⁵ The suspicious mass will be positioned at 10 to 40 mm in axial depth, with standoff used if needed to achieve the desired axial position. Second,

the position of the transducer will be rotated through 90° in steps of 30° to identify the transducer position yielding maximum ARFI peak displacement in the mass. The transducer will be stabilized in this position, with light skin contact, by the sonographer or by using a stereotactic clamp. Third, ARFI and VisR data will be acquired in immediate succession. Fourth, the transducer will be rotated 90°, re-stabilized by the sonographer or by using the stereotactic clamp, and ARFI and VisR data will be acquired in the new transducer position to enable DDAI analysis. Finally, the evaluated mass will undergo clinically indicated biopsy with histological evaluation to determine if it is benign or malignant.

The ultrasound data will be processed to calculate the following outcome metrics: peak displacement (PD), displacement at a given time (TD) for ARFI; τ , relative elasticity (RE), relative viscosity (RV), and tissue mass (TM) for VisR; ratio of ARFI PD and ratio of VisR RE values at 90° versus 0° transducer orientations for DDAI. These eight outcome metrics, alone and in combinations, will be statistically correlated with biopsy finding of malignant or benign.

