6.3.1.3 What is the combined diagnostic accuracy of ultrasound metrics and mammography?

We will select ultrasound metrics with an AUC exceeding 0.75 in C.1.a-b, and their combined diagnostic accuracy with mammography measures (mass size, density, shape, and margins) will be analyzed in separate ROC curves.

6.3.1.4 Which cutpoints for ultrasound metrics detect malignancy with optimum sensitivity and specificity?

Best-balanced cutpoints from the highest performing ultrasound metrics in 6.3.1.1 will be derived from ROC curves, using Youden's Index. These cutpoints will be used to analyze the PPV.

6.3.2 Aim #2: Correlate ultrasound-derived stiffness, elasticity, viscosity, and anisotropy with response to treatment.

In 40 women with newly diagnosed invasive breast cancer who are scheduled to begin clinically indicated NAC, ARFI, VisR, and DDAI imaging will be performed (as described in Aim #1) at baseline, early within each chemotherapy type, and at the conclusion of each chemotherapy type over the course of treatment.

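### Aim 1 takes malignant or benign from the biopsy result, so a cancer found at later excision of the imaged mass would be analysed as benign; PPV at a given cutpoint is then too low, and the effect on AUC has no fixed sign

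*Combined protocol and SAP*

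**What the plan says.** The Aim 1 reference standard appears in four places.

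- Section 1.1 (synopsis) is the broadest: diagnostic accuracy is analysed "with malignancy confirmed by histology as the outcome".
- Section 2.1 narrows this to the biopsy: "the evaluated mass will undergo clinically indicated biopsy with histological evaluation to determine if it is benign or malignant".
- Section 6.3.1 repeats that sentence and says that the eight metrics "will be statistically correlated with biopsy finding of malignant or benign".
- Section 4.4 says that records are reviewed, "including their pathology report from biopsy and information about treatment", and then that "Malignancy will be determined as indicated by the pathology report". The only pathology report it names is the one from biopsy.

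No section says how to label a mass that is benign or indeterminate on biopsy and malignant when excised. None sets a date up to which later histology counts. Section 4.2 gives Aim 1 participation as about 15 minutes. For the cutpoints chosen by Youden's Index, section 6.3.1.4 adds: "These cutpoints will be used to analyze the PPV". Section 6.2 projects 12 malignancies among the 40 women.

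**The concern.** In a diagnostic accuracy study every Aim 1 result rests on the reference label. Under the operative text, a cancer that biopsy missed and excision later found stays in the benign group. If the ultrasound metric flagged it, the metric is charged with a false positive. If the metric did not flag it, a missed cancer is counted as a true negative. With 12 malignancies projected, one to three wrong labels can move PPV visibly, and PPV is the quantity that section 6.3.1.4 derives from the cutpoints. The synopsis wording would allow surgical histology to count, but the analysis sections do not carry it through.

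**Working it through.** **Inputs.** From section 6.2: 12 malignant, 28 benign, AUC 0.70, 95% CI 0.51 to 0.89. Assumed, because the documents give no figure: k = 1, 2 or 3 of the 28 biopsy-benign masses prove malignant at excision, and sensitivity s and specificity sp are both 0.70 or both 0.80.

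**The plan's own interval.** Hanley-McNeil with A = 0.70: Q1 = A/(2−A) = 0.5385 and Q2 = 2A²/(1+A) = 0.5765. Variance = [0.21 + 11(0.5385−0.49) + 27(0.5765−0.49)]/(12×28) = 0.00916, so SE = 0.0957. The CI is 0.70 ± 1.96×0.0957 = 0.512 to 0.888, which reproduces 0.51 to 0.89. The half-width is 0.19.

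**PPV at a fixed cutpoint.** Relabelling does not change which masses test positive. So correct PPV minus biopsy-label PPV = (missed cancers testing positive)/(all masses testing positive), which cannot be negative.

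*Case A: missed cancers score like detected ones.* All positives D = s(12+k) + (1−sp)(28−k). Biopsy-label PPV = 12s/D; correct PPV = s(12+k)/D. Biopsy-label specificity = [sp(28−k) + (1−s)k]/28.

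| s = sp | k | D | PPV, biopsy label | PPV, correct | Difference | Specificity, biopsy label |
|---|---|---|---|---|---|---|
| 0.70 | 1 | 17.2 | 0.49 | 0.53 | 0.04 | 0.69 |
| 0.70 | 2 | 17.6 | 0.48 | 0.56 | 0.08 | 0.67 |
| 0.70 | 3 | 18.0 | 0.47 | 0.58 | 0.12 | 0.66 |
| 0.80 | 1 | 15.8 | 0.61 | 0.66 | 0.05 | 0.78 |
| 0.80 | 2 | 16.4 | 0.59 | 0.68 | 0.10 | 0.76 |
| 0.80 | 3 | 17.0 | 0.56 | 0.71 | 0.14 | 0.74 |

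*Case B: missed cancers score like benign masses.* Take AUC 0.70 and a balanced cutpoint under an equal-variance binormal model, so s = sp = 0.645. Biopsy-label PPV is 0.437; correct PPV is 0.457, 0.478 and 0.498 for k = 1, 2, 3. The differences are 0.02 to 0.06. Specificity is unchanged. Sensitivity is overstated: 0.645 against 0.622, 0.603 and 0.587.

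**AUC.**

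- Case A: biopsy-label AUC = (1−k/28)A + (k/28)0.5. From A = 0.70 it reads 0.693, 0.686, 0.679. From A = 0.80 it reads 0.789, 0.779, 0.768. The shift is at most −0.02 and −0.03 respectively.
- Case B: correct AUC = (12A + 0.5k)/(12+k), while the biopsy label still gives A. At k = 3 this is 0.660 against 0.70, a shift of +0.04. For A = 0.80 it is (9.6+1.5)/15 = 0.74 against 0.80, a shift of +0.06.
- Around A = 0.70, the bias is zero when the AUC of missed cancers against benign masses is about 0.63 to 0.64.

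**The cutpoint the plan will use.** Section 6.3.1.4 takes the Youden cutpoint and the PPV from the same 40 women, which is optimistic in itself. In simulation (12 detected cancers, binormal scores, AUC 0.70, missed cancers like detected ones), mean biopsy-label PPV against true PPV at the chosen cutpoint was 0.54 against 0.48 (k = 1), 0.53 against 0.51 (k = 2) and 0.52 against 0.53 (k = 3). With corrected labels at k = 1 it was about 0.56 against 0.48. The label error therefore lowers PPV relative to correctly labelled data, but the optimism can outweigh it.

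**The case against.** The strongest case against acting has four parts.

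1. **Direction.** A reader might infer that the biopsy-only label pulls PPV, specificity and AUC all downward, with AUC shrinking toward 0.5. The documents do not support that. It requires missed cancers to score on ultrasound like detected ones, and nothing in the plan says so. In Case B AUC and sensitivity are overstated and specificity is untouched. This objection stands.
2. **Comparison with the truth.** A reader might also infer that the published PPV will lie below the true PPV. Under the same-sample Youden procedure it often lies above. What holds is narrower: PPV is lower than correct labels would give at the same cutpoint or in the same sample. Relabelling does not cure the optimism.
3. **Size.** The count of 1 to 3 is an assumption, and no passage says that any biopsy-benign mass is excised. With D = 17.2 positives and PPV 0.488, the Wilson interval has centre (0.488 + 3.84/34.4)/(1 + 3.84/17.2) = 0.49 and half-width 0.21, so about 0.28 to 0.70. The shift is small beside that, in a study that section 1.4 calls exploratory. This is fair as to weight, but imprecision does not justify an avoidable wrong label.
4. **The remedy.** Only masses selected for excision receive the second standard, which is differential verification. Section 4.4 also gives the purpose of the record review as NAC response ("Patient's medical record will be reviewed to assess response to neoadjuvant chemotherapy"), so later Aim 1 surgical records may not yet be collected. Both points stand and belong in the fix.

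It can also be said that the synopsis leaves room for surgical histology. It does, but sections 2.1 and 6.3.1 name the biopsy finding as the outcome analysed.

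**Conclusion.** The point holds in a limited form. On the operative text a cancer found at excision of the imaged mass would be scored as benign, and this does not match the synopsis.

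If 1 to 3 of 28 masses are upgraded:

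- PPV at a fixed cutpoint is understated by 0.04 to 0.12 (sensitivity and specificity 0.70) or 0.05 to 0.14 (0.80) when missed cancers resemble detected ones, and by about 0.02 to 0.06 (AUC 0.70) when they resemble benign masses.
- Specificity falls by 0 to 0.04 at 0.70 and by up to 0.06 at 0.80.
- AUC shifts by about −0.02 to +0.04 around 0.70 and −0.03 to +0.06 around 0.80, small against a half-width of 0.19.

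With no upgrades nothing changes. The figures rest on the assumed count, on the two scoring scenarios, and on a cutpoint held fixed. This is an inexpensive improvement to the reference standard and does not show that the Aim 1 results would be invalid.

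**What to change.** In sections 2.1, 4.4 and 6.3.1, define the Aim 1 outcome as final histology of the imaged mass: malignant if the biopsy, or any standard-of-care excision of that mass charted by a prespecified date before data lock, shows malignancy; otherwise benign. State that labels are assigned without reference to the ultrasound metrics, since section 1.4 describes the study as unblinded. Extend the record review in 4.4 to cover this for Aim 1.

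Report the biopsy-only label as a sensitivity analysis, give the number of masses with excision histology and the number relabelled, and acknowledge the differential verification. State separately that PPV at a same-sample Youden cutpoint is optimistic under either label.

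The cost is one extra chart check per biopsy-benign woman (28 on the plan's projection) and a short wait before Aim 1 data lock. No procedure, visit or change in care is added.
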